## 11.2 ADVERSE EVENTS

Adverse event summaries will include treatment emergent AEs. Treatment emergent AEs include those reported during the parent study for those subjects who were treated with active drug during the parent study. For subjects treated with placebo during the parent study, only those AEs reported during the TDE-PH-304 study are considered treatment emergent.

The AEs will be coded using the Medical Dictionary for Regulatory Activities (MedDRA) and all summaries will utilize the preferred term (PT) and/or System Organ Class (SOC). The correspondence of raw AE terms to PTs and SOCs will be listed. All AEs and serious AEs will be listed by subject, including onset date/day, cessation date/day, verbatim term, PT, SOC, seriousness, severity, relationship to study drug, frequency, and action taken with study drug. The summaries of AEs will be provided by previous study and overall. The summaries of AEs, serious AEs, severe AEs, AEs reasonably or possibly related to study drug, and AEs leading to permanent discontinuation of study drug will include the number of subjects (percent of subjects) and number of events for each reported PT. The summary of AEs by body system will include the same statistics, but will group the PTs by their respective SOCs.

The summary of AEs by exposure will include the number of subjects (percent of subjects) and number of events for each reported PT, as well as the number of events per patient year of exposure. Note that only those subjects with calculated exposure will have AEs contributing to this summary.

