4 SUBJECT ELIGIBILITY

4.1 Subject Inclusion Criteria

A subject is eligible for inclusion in this study if all of the following criteria apply:

1. The subject has remained on study drug and completed all assessments during the Treatment Phase of the previous study (TDE-PH-202, TDE-PH-203, TDE-PH-205, TDE-PH-301, TDE-PH-302, or TDE-PH-308 (or other studies evaluating PAH))
OR
The subject permanently discontinued study drug during the Treatment Phase of the previous study (TDE-PH-301, TDE-PH-302, or TDE-PH-308) due to clinical worsening, completed premature termination assessments prior to discontinuing study drug, completed all remaining scheduled study visits AND received placebo during the Treatment Phase of the previous study (TDE-PH-301, TDE-PH-302, or TDE-PH-308).
OR
The subject was randomized into Dose Group 1 or Dose Group 2 in the TDE-PH-202, permanently discontinued study drug during the 12-week Treatment Phase due to clinical worsening, completed all premature termination assessments prior to discontinuing study drug and completed all remaining scheduled study visits and assessments (with the exception of the hemodynamic measurements) through Week 12. Such subjects should start treatment with UT-15C in the open-label study at 0.25 mg BID.
2. The subject voluntarily gives informed consent to participate in the study.
3. Women of child bearing potential include any female who has experienced menarche and who has not undergone successful surgical sterilization (hysterectomy, bilateral tubal ligation or bilateral oophorectomy) or is not postmenopausal [defined as amenorrhea for at least 12 consecutive months]. Sexually active women of childbearing potential must use two effective forms of contraception during the length of the study. Medically acceptable forms of effective contraception include: (1) approved hormonal contraceptives (such as birth control pills), (2) barrier methods (such as a condom or diaphragm) used with a spermicide, (3) an intrauterine device (IUD), (4) partner vasectomy, or (5) abstinence. Males participating in the study must use a condom during the length of the study, and for at least 48 hours after discontinuing study medication.

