4.2 Subject Exclusion Criteria

1. The subject permanently discontinued study drug during the previous study (TDE-PH-202, TDE-PH-203, TDE-PH-205, TDE-PH-301, TDE-PH-302, or TDE-PH-308) due to treatment related adverse events.
2. The subject permanently discontinued study drug during the Treatment Phase of the previous study (TDE-PH-202, TDE-PH-203, TDE-PH-205, TDE-PH-301, TDE-PH-302, or TDE-PH-308) due to clinical worsening (as defined in those study protocols) and did not undergo premature termination assessments prior to discontinuing study drug, and/or did not complete all remaining study visits through the final scheduled visit.
3. The subject permanently discontinued study drug during the Treatment Phase of the previous study (TDE-PH-301, TDE-PH-302, or TDE-PH-308) due to clinical worsening, completed premature termination assessments prior to discontinuing study drug, completed all remaining scheduled study visits AND received UT-15C SR during the Treatment Phase of the previous study (TDE-PH-301, TDE-PH-302, or TDE-PH-308).

Subjects enrolled in the TDE-PH-202 study who were randomized into the iMTD group who clinically worsen may not participate. Subjects who permanently discontinue study drug during

the 12-week Treatment Phase due to treatment related adverse events are not eligible even if they complete all remaining scheduled study visits. Subjects who permanently discontinue study drug during the 12-week Treatment Phase and do not undergo premature termination assessments prior to discontinuing study drug and/or who do not complete all remaining study visits through the Week 12 visit are also not eligible.

4. The subject must not have developed any concurrent illness or condition during the conduct of the previous study, including but not restricted to, sleep apnea, chronic renal insufficiency, anemia, uncontrolled systemic hypertension or left sided heart disease, unless their physician feels that entry into this study would not be detrimental to their overall health.

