#### **7 ANALYSIS POPULATIONS**

All available data from all subjects enrolled in the TDE-PH-304 study will be used as detailed in this analysis plan. Additionally, subjects who were treated with active drug during the parent study and who enrolled in the TDE-PH-304 study will have the data from the parent study included in the data analyses and listings for this study, as detailed in this SAP.

Subjects who were treated with placebo during the parent study and who enrolled in the TDE-PH-304 study will have baseline data only from the parent study included in the data analyses and listings for this study, as detailed in this SAP.

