## **8 GENERAL CONSIDERATIONS FOR DATA ANALYSES**

All available data for subjects enrolled in TDE-PH-304 (regardless of treatment with active drug) will be included in each soft lock and will be listed. All available data for enrolled subjects who were treated with active drug in study TDE-PH-304 will be summarized, as detailed in this SAP. Subjects from the 200 series studies (TDE-PH-202, TDE-PH-203, and TDE-PH-205) that enrolled into the TDE-PH-304 study will be pooled for summarization purposes with the two de novo subjects previously enrolled in the TDE-PH-301 study. These two de novo subjects were initially enrolled in TDE-PH-301, but were later withdrawn from that study following a temporary drug recall in June 2006 and were subsequently directly enrolled in the TDE-PH-304 OL study. Likewise, subjects from studies TDE-PH-301 and TDE-PH-308 will be pooled for summarization purposes.

In general, listings will be sorted by subject number and scheduled assessment (if applicable). Listings will include assessment date, assessment time (if available), and study day. For data collected on a fixed schedule, the assessment identifier will also be included on the listing.

In general, the data will be summarized by scheduled assessment (if applicable). For continuous variables, the summary statistics will include the mean, standard deviation, standard error, median, lower quartile, upper quartile, minimum, and maximum. Minimums and maximums will be expressed using the level of precision in which the variable was collected. All other statistics will be rounded, using an additional decimal point. For discrete variables, summaries will include the frequency and percent in each category. Percentages will be rounded to a whole number. Whenever practical, categories of discrete variables will be ordered and labeled as they appear in the case report form (CRF), and all categories represented on the CRF will be included in summaries, even when they do not apply to any subjects in the study.

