## 11 SAFETY ANALYSES

### 11.1 EXTENT OF EXPOSURE

Study drug exposure will be listed, including subject number, previous study, concomitant medication use, BID to three times daily (TID) transition, exposure (weeks), and categorical exposure (by visit). Exposure is calculated as the time exposed to active study drug. For subjects treated with active drug during the parent study, exposure calculations will include their exposure during the parent study. For subjects treated with placebo during the parent study, exposure calculations will include only the exposure to active drug during the OL study. The summary of disposition and study drug exposure will detail the number (percent) of subjects who died during the study, as well as the study drug exposure both by categorical visits ( $\geq 3$  months,  $\geq 6$  months, etc.) and using descriptive statistics. The total study drug exposure (pt-years) will also be displayed.

Study drug dosing will be summarized at each visit by previous study and overall. The summary will include a categorical summary of current status (in study, death, progression of PAH, AE, consent withdrawn, lost to follow-up, discontinued for other reasons, etc.) and study drug dose (<1 mg, 1-<2.5 mg, 2.5-<5 mg, 5-<10 mg, 10-<20 mg, 20-<30 mg BID/TID), as well as a descriptive statistics summary of study drug dose (mg BID/TID).

Study drug dosing will also be summarized at each visit by PAH background medication use, grouping subjects into monotherapy and combination therapy groups. The summary table will mimic that presented in the summary of study drug dosing by previous study, but will produce a separate summary table for each PAH background medication use group.

The summary of BID to TID transition will detail the number (percent) of subjects who completed this transition and who had to transition back to BID (if applicable), and descriptive statistics on the doses both before and after the transition by previous study and overall. All of these summaries will be provided by previous study and overall.

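### Read as stopping from first dose of UT-15C SR, the discontinuation-AE percentages in Table 14.3.1.7 are too low, because ex-active subjects had to stay on drug in the parent study to be counted

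*SAP*

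**What the plan says.** **Counting rules.** SAP 11.2: "Treatment emergent AEs include those reported during the parent study for those subjects who were treated with active drug during the parent study". For ex-placebo subjects, only AEs reported in TDE-PH-304 count. SAP 11.1 treats time the same way: "For subjects treated with active drug during the parent study, exposure calculations will include their exposure during the parent study".

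**Who is counted.** SAP 7 limits the parent-study contribution to active-treated subjects "who enrolled in the TDE-PH-304 study will have the data from the parent study included in the data analyses and listings". SAP 8 adds: "All available data for enrolled subjects who were treated with active drug in study TDE-PH-304 will be summarized".

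**Who can enrol.** The main route in Protocol 4.1 reads: "The subject has remained on study drug and completed all assessments during the Treatment Phase of the previous study". Exclusion 1 in Protocol 4.2 reads: "The subject permanently discontinued study drug during the previous study (TDE-PH-202, TDE-PH-203, TDE-PH-205, TDE-PH-301, TDE-PH-302, or TDE-PH-308) due to treatment related adverse events". The text after exclusion 3 repeats that subjects who permanently stop during "the 12-week Treatment Phase due to treatment related adverse events are not eligible even if they complete all remaining scheduled study visits". Exclusion 3 also removes 301, 302 and 308 subjects who stopped for clinical worsening, "completed all remaining scheduled study visits AND received UT-15C SR during the Treatment Phase of the previous study". The one route for an active-exposed subject who stopped is clinical worsening in TDE-PH-202 Dose Groups 1 or 2.

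**How it is shown.** AE summaries are by previous study and overall (SAP 11.2). TDE-PH-301 and 308 are pooled, and the 200-series studies are pooled together with two de novo subjects (SAP 8). By contrast, SAP 10.1 splits 6MWD and Borg by treatment assignment in the previous study (Tables 14.2.1.3 and 14.2.1.4).

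**The concern.** For an ex-active subject the AE count starts at a dose given before enrolment, while enrolment itself required getting through that period on drug. A treatment-related AE that ended treatment in the parent period cannot appear in the table, because the subject who had it is not there. Ex-placebo subjects are counted from their first active dose, early stops included. Putting both in one column gives a percentage that belongs to neither group and depends on the active/placebo mix of each parent study, so columns are not comparable with each other.

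Stopping for AEs is a central tolerability result for a drug that is titrated to effect and side effects. SAP 5 says that these outputs support regulatory submissions. Because the events are labelled treatment emergent from the first active dose, a reader may well take the percentage as tolerability from the start of treatment.

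**Working it through.** **1. Is there a figure to reproduce?** No. SAP 6 gives about 900 subjects as an expectation, not from a power calculation. Neither document gives parent-study discontinuation rates or the active/placebo split.

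**2. Who can contribute an early stop to Table 14.3.1.7?**

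| Subject | Counting starts | Early AE stop can appear? |
|---|---|---|
| Ex-active, 301/302/308 | First parent-study dose | No: had to remain on drug |
| Ex-active, 200-series | First parent-study dose | No, apart from the next row |
| TDE-PH-202 Dose Group 1/2 restarter | First parent-study dose | Only a stop for clinical worsening |
| Ex-placebo | First active dose in TDE-PH-304 | Yes |

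The 301/308, 302 and overall columns mix the first and last rows. The 200-series parents are open-label (SAP 3), so apart from the two de novo subjects that column holds no new starters.

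**3. Direction.** Let a be the ex-active share of enrollees, e the proportion stopping for an AE in the parent-length early period, and l the proportion of the remainder stopping later. Assume e and l are the same for both groups once on active drug.
- From first dose: p = e + (1 − e)·l
- Shown: s = (1 − a)·p + a·l
- Relative shortfall: (p − s)/p = a·e·(1 − l)/p

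This is positive whenever a > 0, e > 0 and l < 1.

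**4. Illustrative size.** All inputs are assumed.
- a = 60%, e = 10%, l = 10%: p = 0.10 + 0.90 × 0.10 = 19%; s = 0.40 × 0.19 + 0.60 × 0.10 = 13.6%; shortfall 0.054/0.19 = 28%.
- Grid of a = 50, 60, 67%; e = 5, 10, 15%; l = 5, 10, 20%: from 8.3% (50, 5, 20: 24% shown as 22%) to 49.6% (67, 15, 5: 19.25% shown as 9.7%).
- Higher later stopping, with a = 50% and e = 5%: l = 30% gives 33.5% shown as 31.75%, a shortfall of 5.2%; l = 40% gives 43% shown as 41.5%, a shortfall of 3.5%.

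**5. Cross-check by adding back the missing subjects.** With 900 enrollees and a = 60% there are 540 ex-active subjects. If 10% of active subjects stopped early, 540 × 0.10/0.90 = 60 are missing. The shown 13.6% is 122.4 subjects, and (122.4 + 60)/960 = 19.0%, which agrees with step 4. Starting instead from a shown 10%, the same method gives 11.4% (a = 50%, 3% missing), 15.6% (60%, 10%) or 23.4% (70%, 20%).

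**6. Does the argument carry over to any-AE rates?** Assume a = 60%, a 12-week early period, and missing subjects exposed for 6 weeks at k times the AE rate of the others. With T and t the patient-years of enrollees and missing subjects, the all-exposed to shown ratio is (T + k·t)/(T + t). For 5 to 20% missing it is 1.03 to 1.14 at k = 3, 1.02 to 1.07 at k = 2, 1.00 at k = 1, and 0.97 to 0.99 at k = 0.5. The direction depends on k, which the documents do not give.

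**The case against.** The objective in Protocol 2.1 and SAP 2.1 is long-term safety in the subjects eligible for this extension. For them the percentages are right, and the SAP does not claim to estimate stopping among everyone who ever started UT-15C SR. The eligibility rules are reproduced in SAP 12.1, SAP 9.1 tabulates parent treatment groups and reasons for discontinuation, and SAP 8.1 allows further subgroups. **This stands in part:** the matter is one of interpretation, not a wrong computation. But none of those provisions separates the two kinds of subject in an AE table or warns the reader about the selection.

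Stronger readings are tempting, and the documents do not support them:

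- *Early AE rates are understated too.* No early-interval rate is planned, and step 6 shows that the direction rests on an unknown.
- *Table 14.3.1.9 is diluted by event-free time.* It covers all AEs per patient-year and takes in ex-active subjects' parent-study events as well as their time.
- *The shortfall is at least 8%.* That floor comes only from capping later stopping at 20%. Protocol 3.6 foresees at least 36 months and open-ended follow-up, so later stopping could be higher and the shortfall smaller.
- *Ex-placebo subjects give an unselected first-dose estimate.* They too had to complete the parent study, or worsen clinically on placebo and complete all visits, and exclusion 1 is not limited to active drug.

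**Conclusion.** The point holds for the percentage with AEs leading to permanent discontinuation, read as from first dose of UT-15C SR. The selection follows from the text alone. The shortfall exists whenever some active subjects stopped early for a treatment-related AE and, in the simple model above, early and later stopping risks are alike in the two groups. It affects the 301/308, 302 and overall columns through mixing; the 200-series column is almost wholly pre-selected. The size cannot be derived from the documents: 19% against 13.6% is an illustration, and other plausible inputs give anything from a few percent to about half in relative terms. As a description of TDE-PH-304 enrollees the figures are correct. The change should be made before the tables are used to describe tolerability.

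**What to change.** In SAP 11.2 and the table list in SAP 12.2:

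1. Present the AE tables, at least 14.3.1.7 and 14.3.1.9, by parent-study treatment (ex-placebo new starters against ex-active) within previous study and overall. Identify TDE-PH-202 Dose Group 1/2 restarters separately, since they had earlier active exposure and fit neither group.
2. Base any statement about stopping for AEs from first dose on the ex-placebo new starters, noting that they are themselves selected on the placebo period.
3. Footnote these tables: active subjects who permanently stopped for treatment-related AEs in the parent studies are not included.

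Starting the ex-active count at TDE-PH-304 entry is not a substitute. Table 14.3.1.7 reports subjects, percentages and events; there are essentially no parent-period stops to remove and the denominator stays the same, so the 13.6% in the illustration would remain 13.6%.

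Cost: SAP wording, a split of the kind already planned for 6MWD and Borg, wider tables, and a less favourable figure for new starters. No new data or visits are needed.

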1.2.2 UT-15C SR Clinical Pharmacology

In solution, both treprostinil sodium and treprostinil diethanolamine are disassociated from their respective salt counter-ions and exist as the freely ionized form of treprostinil. As a result, the bioactive form present in the bloodstream is identical irrespective of the selection of the counter-ion. Given this premise, the development of this new diethanolamine salt of treprostinil is expected to retain the bioactivity and safety profile of treprostinil sodium.

The most frequent AEs associated with Remodulin in clinical trials of patients with PAH were related to the pharmacological properties of Remodulin and were generally not serious. These prostacyclin-related AEs included diarrhea, headache, and nausea. Remodulin has not been associated with any significant changes in laboratory parameters or end-organ toxicity. The safety profile noted in the open label extension study, with much longer durations of exposure and a larger, more diverse patient population, was consistent with the profile noted in the controlled trials. To date, well over 10,000 subjects and patients have been exposed to Remodulin. This number includes patients who have received single administration, to patients receiving continuous infusion for greater than 10 years.

[figure not shown]
UT-15C has been administered to approximately 1,600 subjects in phase I-III clinical trials. UT-15C doses of up to 3 mg twice daily (BID) have been administered to healthy volunteers and patients with PAH have received up to 22 mg BID in the ongoing phase III development program. The longest individual exposure is now greater than five years.

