### **8.1 EXAMINATION OF SUBGROUPS**

All summaries will be provided by previous study and overall to allow examination of impact from previous study. Other exploratory subgroup analyses will be performed as data permit.

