## 10.2 CLINICAL EVENTS

Clinical events, including death, study discontinuation for any reason, addition of PAH therapy, and addition of parenteral PAH therapy, will be listed, including date of each event, if applicable, as well as the subject's previous background therapy status (naïve, single background therapy, or double background therapy). Note that events may have occurred during the parent study for those subjects treated with active drug during the parent study, thus event data from the parent study will be included in these data analyses. The following combinations of clinical events will be utilized for summarization and plotting purposes, separately:

- Study discontinuation for any reason
- Death or discontinuation due to disease progression
- Death, discontinuation due to disease progression or addition of PAH therapy
- Death, discontinuation due to disease progression or addition of parenteral PAH therapy
- Death

Summary tables will be produced by previous study and overall and will display the number (percent) of subjects who experienced each event combination detailed above. Kaplan-Meier (K-M) curves for the above combinations of clinical events will be provided separately. Each K-M plot will include a time to clinical event curve for each of the previous studies overlaid on the same plot.

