## 11.3 DISEASE RELATED EVENTS

The disease-related events reported during the TDE-PH-304 study will be listed, including subject number, previous study, and symptom. The summary will include the number (percent) of subjects who reported each symptom by previous study and overall.

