#### 11.4 DEATHS

All deaths occurring within 30 days of study TDE-PH-304 participation will be listed by subject, including previous study, first dose, last dose, discontinuation date, reason for discontinuation, date of death, day of death, and cause of death. The summary of deaths will be presented by previous study and overall and will include the number (percent) of subjects who died within 30 days of study participation and their causes of death.

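### The serious, severe, related and discontinuation AE tables and the disease-related event table have no person-time denominator, so their previous-study columns partly reflect length of follow-up

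*SAP*

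**What the plan says.** SAP 8.1 gives the purpose of the column layout: "All summaries will be provided by previous study and overall to allow examination of impact from previous study". SAP 11.2 applies it to AEs: "The summaries of AEs will be provided by previous study and overall".

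The statistics planned in the affected tables are:

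- **Serious, severe, related and discontinuation AEs** (SAP 11.2; Tables 14.3.1.3 to 14.3.1.7): these "will include the number of subjects (percent of subjects) and number of events for each reported PT". Table 14.3.1.4 (related serious AEs) appears only in the table list, and I take it to have the same layout.
- **Disease-related events** (SAP 11.3; Table 14.3.1.8): "The summary will include the number (percent) of subjects who reported each symptom by previous study and overall". No event count and no rate is planned.

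Three planned outputs do take account of follow-up:

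- The AE summary by exposure (Table 14.3.1.9) repeats the counts by preferred term, "as well as the number of events per patient year of exposure". It covers all AEs, with no split by seriousness, severity, relatedness or discontinuation.
- Table 14.1.2 (SAP 11.1) shows total patient-years by previous study.
- SAP 10.2 plans Kaplan-Meier plots, one of them for death alone (Figure 14.2.1.7.5): "Each K-M plot will include a time to clinical event curve for each of the previous studies overlaid on the same plot".

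**The concern.** The percentage of subjects who have ever had an event cannot fall as follow-up lengthens, and it rises at any constant risk. If previous-study columns differ in follow-up, a column can look worse because it was watched longer, and a real difference can be masked in the same way. The same applies between one soft lock and the next for a fixed set of subjects.

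This matters because long-term safety is a stated objective, and serious AEs and AEs leading to discontinuation are central to it. SAP 8.1 invites the reader to compare the columns. SAP 5 says the repeated locks serve to monitor long-term safety.

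**Working it through.** **Step 1. Is follow-up equal across columns by design?** No.

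- SAP 3 sets no common end date. Yearly visits continue past 36 months until approval or until the sponsor stops the study.
- SAP 5 allows soft locks as often as yearly, so subjects are cut off at different lengths of follow-up.
- SAP 11.1 and 11.2 count parent-study exposure and AEs only for subjects on active drug in the parent study. SAP 3 describes TDE-PH-202, TDE-PH-203 and TDE-PH-205 as open-label, while TDE-PH-301, TDE-PH-302 and TDE-PH-308 had placebo arms. The 200-series column therefore carries parent-study time in a different proportion from the other columns.

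These features make unequal follow-up likely. They do not give its size, and no document states follow-up per column.

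**Step 2. What does unequal follow-up do to the crude percentage?** The plan has no figure of its own to reproduce. SAP 6 bases the sample of about 900 on expected enrollment, and no event rate is given. All values below are assumptions: event hazard h per year, independent dropout hazard d per year, follow-up T years.

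- Crude proportion = h/(h+d) × (1 − exp(−(h+d)T))
- Person-years to first event per subject = (1 − exp(−(h+d)T))/(h+d)
- First-event rate = crude proportion ÷ person-years = h

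Worked case, h = 0.10:

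- d = 0, T = 1: 1 − exp(−0.10) = 9.5%
- d = 0, T = 3: 1 − exp(−0.30) = 25.9%
- d = 0.30, T = 1: 0.25 × (1 − exp(−0.40)) = 8.2%
- d = 0.30, T = 3: 0.25 × (1 − exp(−1.20)) = 17.5%

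Across a range of hazards:

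| h per year | 1 y, d = 0 | 3 y, d = 0 | 1 y, d = 0.30 | 3 y, d = 0.30 |
|---|---|---|---|---|
| 0.02 | 2.0% | 5.8% | 1.7% | 3.9% |
| 0.05 | 4.9% | 13.9% | 4.2% | 9.3% |
| 0.10 | 9.5% | 25.9% | 8.2% | 17.5% |
| 0.20 | 18.1% | 45.1% | 15.7% | 31.1% |

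At equal risk the 3-year column shows 2.5 to 2.9 times the 1-year percentage without dropout, and 2.0 to 2.6 times with dropout of 0.15 to 0.30 per year.

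Event counts behave alike. At 0.10 events per year, 100 subjects yield 10 events in 1 year and 30 in 3 years without dropout, or 8.6 and 19.8 with dropout of 0.30.

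**Step 3. How much does counted parent-study time alone add?** Take 12 weeks, the TDE-PH-202 Treatment Phase length in Protocol 3.5, purely as an example. At h = 0.10 and T = 1 without dropout, the percentage moves from 9.5% to 1 − exp(−0.10 × (1 + 12/52)) = 11.6%. This is small beside differences of a year or more in follow-up.

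**Step 4. Does a first-event rate remove the effect?** Under these assumptions it does. At h = 0.10 the 1-year and 3-year columns both return 0.10 per patient-year, with or without dropout.

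**Step 5. Do the planned outputs already supply this?**

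- Table 14.3.1.9 counts all AEs, repeats included, so no rate for a subset can be read from it.
- Event counts in Tables 14.3.1.3 to 14.3.1.7 can be divided by the patient-years in Table 14.1.2. The result is a crude event rate, is not planned, and is not first-event incidence.
- For disease-related events this division is not possible, since no event counts are planned. The windows also differ: SAP 11.3 counts events during TDE-PH-304, while SAP 11.1 exposure includes active parent-study time. Protocol 9.1.3 keeps progression events out of the AE pages unless they are serious, unusual or possibly caused by the drug, so Table 14.3.1.9 misses the rest.

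**The case against.** The other side has several good points.

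- **Deaths.** SAP 11.4 gives a crude summary that "will include the number (percent) of subjects who died within 30 days of study participation and their causes of death", and a reader might infer that mortality rests on crude percentages. It does not: Kaplan-Meier curves of death by previous study are planned, and they handle unequal follow-up better than a rate would. Only the cause-of-death breakdown stays crude.
- **No comparison possible.** A reader might infer that the AE columns cannot be compared at all. That is too strong. Event counts and patient-years by previous study are both planned, so a crude event rate can be worked out by hand. For AEs leading to discontinuation it should be close to the first-event rate, because the event ends exposure.
- **Evidence of imbalance.** The two subjects affected by the 2006 recall and the later TID entrants from TDE-PH-205 might seem to show staggered follow-up between columns. SAP 8 pools them in one column, so they show nothing of the kind. Protocol 1.2.2 says "The longest individual exposure is now greater than five years", but that is one maximum for the whole program, not follow-up by previous study.
- **Seriousness of disease-related events.** Protocol 9.1.3 sends serious or unusual progression events to the AE tables, so the disease-related event table is not a serious-event output.
- **Descriptive tables.** No hypothesis test is specified for them, and comparing previous studies is not a study objective. No error rate is at risk.

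These points narrow the concern without removing it. SAP 8.1 offers the columns for comparison, the affected tables print no rate, and the SAP already judged exposure adjustment worthwhile for AEs as a whole.

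**Conclusion.** The point holds for Tables 14.3.1.3 to 14.3.1.7 and Table 14.3.1.8. Their crude percentages mix risk with follow-up time, and no planned output gives first-event incidence for these subsets by previous study. The direction of the distortion does not depend on the assumptions. Its size does: a factor of about 2 to 3 between 1 and 3 years of follow-up, for assumed hazards of 0.02 to 0.20 per year and dropout of 0 to 0.30 per year. If follow-up per column proves similar, the effect will be small.

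The consequence is a misleading reading of descriptive columns and of successive locks, with no effect on any test. The change is inexpensive and should be made.

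**What to change.** 1. In SAP 11.2, extend the exposure adjustment of Table 14.3.1.9 to serious, severe, related and discontinuation AEs. Report subjects with a first event per 100 patient-years at risk, with an exact Poisson 95% CI, by previous study and overall. Time at risk ends at the first event or at the end of the table's window.
2. In SAP 11.3, do the same for disease-related events using TDE-PH-304 time only, to match the window in which they are counted. This needs onset dates, which SAP 11.3 does not name among the listed items. If they are unavailable, rely on the footnote in step 3.
3. Footnote the affected tables to say that crude percentages are not comparable across previous-study columns or across locks.
4. In SAP 11.4, cross-refer Table 14.3.2.2 to Figure 14.2.1.7.5. Nothing more is needed for deaths.

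The AE listings already hold onset dates, and the disposition listing holds first and last active-dose dates, so the AE rates need no new data collection. The costs are wider tables and derivation of time to first event for each preferred term in each subset. The rates also bring a constant-rate assumption, which the SAP should state: if events cluster early in treatment, a column with longer follow-up will show a lower rate for that reason alone.
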